To investigate the effectiveness of job crafting intervention program on job crafting behavior, work meaningfulness, change attitude, adaptive and task performance among nurses at Zagazig university hospitals.

Research hypothesis:

1. After program intervention, nurses will demonstrate an increase in job crafting behavior (increasing job Resources, increasing challenging job demands, and decreasing hindering job demands).
2. Nurses participating in the intervention program will report higher levels of work meaningfulness.
3. The experimental group will demonstrate an increase in positive work attitude and decrease in negative work attitude

4. The experimental group will experience a higher adaptive performance and perform higher levels of task performance.
5. An increase in job crafting behavior is related to and predicts work meaningfulness, change attitude, adaptive and task performance among nurses

Subjects and Methods:

Research design:

The study described in ClinicalTrials.gov with the identifier NCT.....utilized a randomized control trials research design.

Administrative & Ethical Steps:

We obtained official written authorization from the Zagazig university hospitals in order to carry out our research, following the approval of ethical considerations. Formal consent and authorization for the study were also acquired from the Research Ethics Committee within the Faculty of Nursing at Zagazig University, Egypt (IRB:). Patients were duly informed about the study's objectives, and we obtained their informed written consent. They were informed of their right to decline participation, with the assurance that their decision would not impact their care. Moreover, patients were assured that they had the option to withdraw from the study at any point, even after initiation, with the assurance of maintaining their privacy and confidentiality.

Study setting :

This study was conducted at the Zagazig University Emergency Hospital, which provides a wide spectrum of health services at El Sharkia Governorate in Egypt. This hospital receives emergency cases and injuries 3 days/week from Zagazig City and other near areas, giving care for about 7.5 million people, according to the hospital most recent statistical data. The hospital is occupied with (185) beds.

Subjects:

Include staff nurses working in different departments of Zagazig University Emergency Hospital.

Sample size :

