We employed the G* Power version 3.1.9.7 software program to calculate the sample size based on the specified parameters.: a total sample size of approximately ..., an effect size of 0.5, α error probability of 0.05, Power (1- β error probability) of 0.95, two groups, three measurements, and a correlation among repeated measures of 0.5. The program recommended a minimum sample size of 140 nurses. However, the researchers decided to recruit 150 nurses for both the control group and the study group.

[figure not shown]
To be eligible for the study, nurses had to be.....

As shown in figure (1), each randomly selected nurses were screened to identify the student who met the predetermined inclusion criteria. Three students refused to participate and were excluded due to lack of inclusion criteria. A comprehensive list of the rest, containing the names and relevant data of all students was compiled. The participants were assigned to either the control or study group using a computer-generated randomization list (....each). This random assignment ensured fairness and minimized bias.nurses were withdrawn from either the control or intervention group

Table 1: Stratified random sample using proportion allocation technique.

Academic Level	Strata according to the department	The Expected population size of each stratum	Proportionate sample size in each stratum
1			
2			
3			
4			

Total	Size of the entire population=	Total sample size = 150
--------------	---------------------------------------	--

Intervention (n=62)
Completed post-intervention assessment=60
Lost or dropped out in second post-test = 2

Control (n=61)
Completed post-intervention assessment=60
Lost or dropped out in second post-test = 1
(Not included in the analyse)

Analyzed (n=60)

Analyzed (n=60)

CONSORT analysis of nurses' enrollment and recruitment process

Follow up

Analysis

Tools of data collection: A questionnaire sheet was used to collect data for this study and composed of five parts:

Part (1): This covers staff nurses ' demographic information such as age, department, education level, years of experience, and previous training in job crafting.

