head nurses of the departments were briefed on the upcoming research. This step was included as this may aid in the effectiveness of the intervention as they may stimulate and motivate the nurses to part-take in the intervention with motivation and enthusiasm. The pre-test forms have been given to nurses to determine their training needs regarding job crafting and job crafting behavior among Nurses. The data were gathered during morning and afternoon shifts for four days / week. The time each staff nurse needed to complete each sheet varied from 25 to 30 minutes. The learning needs of nurses were established based on pre-test results. Accordingly, the program's goals have been set out and the content developed.

Implementation phase: ((please insert in table with sessions name, objective, time, steps).

The training program designed for this study was implemented through twelve sessions, from which three theory and nine practical sessions were held in a room at the worksite. The sessions were conducted outside of working hours in the hospital. These sessions lasted 21 hours; 3 theory hours (one hour for each theoretical session); and 9 practical sessions (two hours for each practical session). Having the whole number of nurses at the same time was difficult, so the nurses were classified into five groups each group consisting of about 16 nurses. All sessions were repeated to the five main groups until 80 nurses completed the entire 21-hours instruction period.

The program includes three main parts;

the first theoretical part covers knowledge of the job crafting, job crafting theory, Job Demands–Resources model, definition work environment, combine work environment and JD- R model. Then, based on examples from structured interviews conducted before the program, examples of job crafting are provided, as well as examples of a work analysis. Success stories of past job crafting behaviors of staff nurses were shared and discussed. This was helpful to reflect on the current work performance, and then made their own individual job crafting plans.

The second practical part was included to guide the employees on how to craft their daily activities and to give them suggestions on craft-able work-related activities as 1- increasing job Resources e.g. ask feedback, ask support, ask for help from colleagues or your leaders if you need help, participate committees, look for trainings, invest in

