relationships, and clean your desk to work more efficiently. 2- increasing challenging job demands e.g. volunteer work for a committee, communication about emotional/serious issues to patients and families, offer to be responsible for making the nursing schedule in a certain month, share your head nurse in writing certain documents, and stay informed about current and recent research.3- decreasing hindering job demands e.g. simplify tasks, work more efficient, let go perfectionism, say 'no', make clear appointments, checking emails only at certain times during the day and make use of relationships. The staff nurses were then asked to conduct a personal work analysis, guided by questions in their personal action plan. They were also provided with a homework papers for a job crafting exercise. Each staff nurse reviewed his/her own job crafting plan individually (20 min); the nurses then shared their reflections as a group (30 min), discussed what job crafting would be feasible and sustainable to practice (35 min), and, finally, made a modified job crafting plan (35 min). Thereby aiming to increase awareness for the utility of job crafting in their work environment.

The third and last part

consisted of setting personal goals. These goals were aimed at the three job crafting dimensions and had to be SMART5. Complementary, the participants had to formulate actions to attain their personal goals. Each staff nurse had one week to attain his or her goal with respect to the corresponding job craft dimension of that week. The researchers used different teaching approaches to attract the attention of nurses and to inspire them to participate, such as seminars, group discussion and brainstorm. The teaching media included: power point, white blackboard and a copy of the program which covered theoretical and practical information about job crafting, Job Demands–Resources model, combine work environment and JD- R model. All data were collected using a self-report questionnaire at baseline, post-intervention, and three-month follow-up.

Evaluation phase: The impact of the educational program was measured during this phase; it was carried out immediately after the program was introduced and followed up after 3 months of implementation using the same method formats used before the program was implemented.

Administrative and ethical considerations:

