Before the research started, ethical approval was given by the Scientific Research Ethics Committee at the Faculty of Nursing-Zagazig University (NO: 056). Participants were

explained the study objective and protocol, and only those who provided informed consent were included. Voluntary participation, autonomy, and confidentiality of the information gathered were confirmed.

Statistical design:

All data were collected, tabulated, and statistically analyzed using version 20.0 of the Social Science Statistical Package (SPSS), quantitative data were expressed as mean \pm SD and range, and qualitative data were expressed as absolute frequencies (number) & relative frequencies (percentage). Paired t-test was used to compare normally distributed variables between two dependent groups. P.

Pearson correlation coefficient has been determined to determine the relationship between different variables of the sample,(+) sign indicates direct correlation and-) (sign indicates reverse correlation, even values close to 1 indicate strong correlation and values close to 0 indicate weak correlation. All testing was two-sided. P-value < 0.05 was deemed statistically significant (S), and p-value < 0.001 was considered highly statistically significant (HS), and p-value ≥ 0.05 was considered statistically insignificant (NS).

References

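### Hypothesis 5 claims that an increase in job crafting predicts the other outcomes, but the only association method stated, an unadjusted Pearson correlation, supports no more than a relation

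*Protocol*

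**What the plan says.** Under Research hypothesis, item 5 reads: "An increase in job crafting behavior is related to and predicts work meaningfulness, change attitude, adaptive and task performance among nurses". It makes two assertions, and their subject is an increase, that is, a change over time.

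The Statistical design section names two inferential methods. One is for paired comparisons: "Paired t-test was used to compare normally distributed variables between two dependent groups". The other is the association method: "Pearson correlation coefficient has been determined to determine the relationship between different variables of the sample". The coefficient is to be read by its sign and its size: "values close to 1 indicate strong correlation and values close to 0 indicate weak correlation". The section does not say which variables or occasions are correlated, whether change scores are used, or whether arm or baseline enters.

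The data would allow more. The Implementation phase states: "All data were collected using a self-report questionnaire at baseline, post-intervention, and three-month follow-up".

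The repeated-measures ANOVA near the end of the document stands in sample-size text for a different trial (a Port Said hospital, 94 nurses). It is not an association method for this study.

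**The concern.** The hypothesis lists prediction in addition to relation, so the analysis should be able to tell the two apart. An unadjusted Pearson coefficient treats its two variables alike. Nothing stated makes one of them the earlier change and the other the later outcome, and nothing removes what both scores owe to the program or to the outcome's own earlier level.

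At stake is the conclusion drawn from hypothesis 5. A significant coefficient could be offered as support for *predicts* when it shows only that two scores go together, in part perhaps because the program moved both. This is a mismatch between a stated hypothesis and a stated method. The choice of visit, pooling and covariates could be settled in an analysis plan that is not shown, and their absence is not the complaint.

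**Working it through.** **Text comparison.** No figure in the protocol has to be reproduced for this point.

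| Part of hypothesis 5 | Covered by the stated method? |
|---|---|
| Related | Yes: sign and strength of r |
| An increase | Not stated: no change score is named |
| Predicts | Not beyond related: no time order or adjustment is stated |

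**What a Pearson test can do.** The test of r and the test of the slope in a one-predictor regression are the same test. In one simulated set of 150 observations both gave p = 3.28e-09, with r² = R² = 0.211. Pearson therefore covers prediction in the unadjusted two-variable sense, which adds nothing to *related*.

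**Illustration of one consequence.** Inputs:
- Sizes: 120 (60 analyzed per arm in the flow chart) and 150 (total in Table 1), taken as 1:1.
- Two-sided 0.05, from Statistical design.
- Correlation of 0.5 between occasions, from Sample size: "two groups, three measurements, and a correlation among repeated measures of 0.5".
- Assumed, not in the protocol: program shifts d1 and d2 in SD units, normal scores, no relation within arm, post-program scores with arms pooled.

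With 1:1 arms and within-arm variance 1, the pooled covariance is d1·d2/4 and the pooled variances are 1 + d1²/4 and 1 + d2²/4. Hence

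r = d1·d2 / √[(d1² + 4)(d2² + 4)].

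- d1 = d2 = 0.5: r = 0.25/4.25 = 0.059.
- d1 = 0.5, d2 = 0.2: r = 0.10/√(4.25 × 4.04) = 0.024.
- d2 = 0: r = 0.

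Simulated probability of p<0.05 (8,000 replicates):

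| Shifts | Pooled Pearson, N=120 / 150 | Arm-adjusted regression, N=120 / 150 |
|---|---|---|
| 0.5 and 0.5 | 9.9% / 11.1% | 4.8% / 5.1% |
| 0.5 and 0.2 | 5.6% / 6.0% | 5.1% / 5.1% |
| 0.5 and 0 | 5.1% / 4.8% | 5.3% / 5.1% |

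Pooled Pearson on change scores stays within 0.012 of the post-score figures, so using change scores without adjusting for arm does not remove the effect. A larger shift gives more (0.8 SD in both: 33% / 40%), but no passage supports that size.

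**Which regression would fit *predicts*.** Suppose the two scores move together at the post-program visit (assumed correlation of innovations 0.3), each carries over to 3 months at an assumed 0.5, and job crafting has no later effect on the outcome. A regression of the 3-month outcome on the change in job crafting that omits the post-program outcome then gives p<0.05 in roughly 36% to 38% of runs at N=150. Adding the post-program outcome brings this to about 5%. That term therefore belongs in the main model.

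**The case against.** A reader might infer that a correlation can never address prediction. That goes too far. Time order comes from the variables entered, and the change in job crafting could be correlated with a 3-month outcome. The protocol does not state that use, and even then the coefficient would be unadjusted.

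It can also be said that the Statistical design section is visibly unfinished (it breaks off after the paired t-test) and that a regression for a non-randomized fifth hypothesis is commonly left to an analysis plan. This stands as far as the details go. It does not remove the mismatch between the claim and the one association method that the protocol chose.

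The percentages measure pooling of arms, not prediction against relation. A pooled lagged regression would show similar inflation. Nor are they a false-positive rate for hypothesis 5 as worded: when both scores shift, the pooled correlation over all nurses is truly non-zero. These objections are right, and the figures serve only to show why arm matters to the interpretation.

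A reader might finally infer that shared training groups make things materially worse, since the protocol says "so the nurses were classified into five groups each group consisting of about 16 nurses" and that "the nurses then shared their reflections as a group (30 min" minutes. These passages show that groups existed and interacted. They give no size for a group effect, and any figure would rest on invented inputs, so none is claimed here.

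**Conclusion.** The point holds in a limited form. The stated association method supports the *related* part of hypothesis 5 and adds nothing for the *predicts* part. The mismatch rests on the text alone and does not depend on the simulation.

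The illustrated consequence is small: about 10% and 11% against a nominal 5% at N=120 and 150, under assumed 0.5 SD shifts in both scores, pooled arms and no relation within arm. It almost vanishes if one shift is small and is absent if only one score shifts. The protocol fixes none of these conditions.

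The documents do not support reading this as a flaw in the evaluation of the program itself. Hypotheses 1 to 4 and the sample size are unaffected, and no passage says that a correlation will be reported as prediction. This is a low-priority change that the sponsor could make.

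**What to change.** Choose one of two options.

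1. **Narrow the claim.** Limit hypothesis 5 to *is related to*, and compute the correlations on change scores as partial correlations given arm.
2. **Keep *predicts* and name a model for it.** For each outcome, regress the 3-month value on the baseline-to-post change in job crafting, adjusted for arm, baseline job crafting, and the baseline and post-program values of that outcome. Report the coefficient with its 95% CI as an exploratory, non-causal association.

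Training-group terms are optional in either case. If they are used, each trained nurse's group must be recorded.

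Cost: the first option is a change of wording and of the correlation computed. The second adds one regression per outcome, on data already planned at the three occasions. Its coefficients may be smaller than pooled correlations, and they answer a within-arm question. Nurses without a 3-month assessment drop out of this analysis.

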Theoretical Framework Job crafting intervention is a training program designed to encourage individuals to proactively redesign their jobs by optimizing available job resources, managing increased job demands, and adapting to new job challenges [34]. Job crafting intervention is based on two main approaches: (1) the Wrzesniewski and Dutton approach, which frames job crafting as proactive changes in task, relational, and cognitive job aspects [10], and (2) the Tims et al. approach, which is based on the Job Demands-Resources (JD-R) theory [7]. Te JD-R theory postulates that individuals require a sufcient amount of job resources to efectively cope withthe demands they encounter in their work. According to this theory, organizations play a

crucial role in providing optimal job demands and resources to their employees. However, individuals also possess the autonomy to proactively modify their job demands and resources, thereby contributing to a better alignment between individuals and their jobs. Consequently, this leads to enhanced optimal functioning within the workplace [35]. Job crafting, when framed within this context, refers to the ability of individuals to change three types of job characteristics: job resources, seeking challenge, and job demands [7]. Previous studies have explored the outcomes of job crafting intervention and demonstrated its positive effect on enhancing work engagement, job performance [29], career satisfaction [36], and well-being [12]. Job crafting intervention increases individuals' awareness of their own preferences and needs, empowering them to take action to make changes. The job crafting intervention provides individuals with specific techniques and tools they can use to identify areas where they can make changes to manage their job resources and demands. Moreover, job crafting intervention encourages them to formulate a job crafting plan, which increases their adherence to job crafting behaviors [37]. Hence, job crafting intervention leads to an increase in job crafting behaviors and all related dimensions. Therefore, the study hypothesized that

Subjects and Methods

3.1. Study Design. This study was a two-arm, parallel, open-label randomized controlled trial (RCT) that conforms to the Consolidated Standards of Reporting Trials (CONSORT) guidelines [44]. The study protocol was registered at ClinicalTrials.gov (Identifier code: NCT05329805; 15/04/2022). **3.2. Participants and Setting.** This study recruited nurses working 12 hours per shift for 186–195 hours a month at one of the universal health insurance hospitals in Port Said Governorate, Egypt. Nurses who were licensed staff nurses, worked in a ward, and had at least 6 months of experience were included in the analysis. In contrast, nurses who were involved in any other intervention program within the last 12 months, working in clinics, or holding an administrative position were excluded. Of the 224 invited participants, 58 did not meet the inclusion criteria, 62 declined to participate, and 10 were piloted. Ultimately, 94 were included

and randomly allocated to the intervention group (n = 47) or the control group (n = 47). Overall, 79 (39 in the intervention group and 40 in the control group) completed the intervention up to T2 data collection. The attrition rate from the baseline (T0) until T2 data collection was 15.95%. Figure 1 illustrates the consort flow diagram of the participants. 3.3. Sample Size Calculation. A prior sample size was estimated using the G*Power 3.1.9.7 Software [45] for repeated measures analysis of variance (ANOVA) design (withinbetween interactions) with effect sizes of 0.26 and was obtained from the meta-analysis on job crafting intervention that included healthcare professionals [29] (α error = 0.001, power = 0.95). A sample of 72 participants (36 for each group) was estimated. Considering the possibility of a 30% attrition rate resulting from high dropout/loss to follow-up among Egyptian participants [46], the recruitment target was 94 participants (47 in each group). 3.4. Randomization and Blinding. An independent researcher randomly assigned the participants to the intervention or control group by using the “Research Randomizer” web-based program [47]. The number of groups needed and the number of potential participants

were input into the program, which generated two sets of 94 unique, sorted numbers arranged from the least to the greatest and allocated randomly to either Group 1 (representing the control group) or Group 2 (representing the intervention group) in a 1 :1 ratio. The allocation sequence was concealed by using opaque sealed envelopes. Blinding was not feasible in this study because the intervention provided was an educational program, which made the blinding of the researcher or the participants to the group allocation difficult [48]. Nevertheless, to minimize the risk of bias, the data collection and analysis were performed by authors (SM, MS, and MZ) were not involved in providing the intervention program conducted. 3.5. Intervention. The job crafting intervention program was developed according to the Michigan Job Crafting Exercise [37] and was operationalized on the basis of the JD-R theory principles [49]. The intervention aimed to train the participants in maximizing their job resources, optimizing the increased job demands, and adapting new job challenges, which may be useful in enhancing their harmonious work passion and

career commitment. Prior to the intervention program, potential participants and nursing managers with different levels were interviewed to understand the work context, which included the following: what does good performance mean from their point of view, what hinders them from doing so, what helps them to provide high-quality care, what tasks represent challenges, and why they did not assume such challenges. This information was utilized to prepare a tailored intervention and customized examples in creating the intervention. Five-expert committee included two nursing administration professors, one nursing manager, and two staff nurses with master's degrees were asked for suggestions on the content and structure of the intervention materials. The intervention materials were modified based on their suggestions and sent back to the committee for approval. Then the intervention materials were pilot tested to ensure their quality and clarity. Thereafter, the intervention was conducted, consisting of a 2-day workshop, 3 weeks of job crafting implementation, and a reflection session. The workshop consisted of four 60–90-minute sessions with 2 sessions per day and 30 min rest between sessions over 2 days. In session 1, the researcher introduced the theoretical background. In session 2, the JDR model was discussed in detail, and the participants were requested to share their personal job crafting experiences. In session 3, they were invited to participate in the Michigan Job Crafting Exercise [37], which included job analysis, personal analysis, and job-personal analysis. As a result of completing the exercise, each participant was expected to be aware of the following: resources that could be increased, the idea that demands could be decreased without interrupting the work, and areas that represent a challenge to them. In the fourth session, the participants were invited to prepare their own "Personal Crafting Plan." Table 1 details the content of the workshop. At the end of the workshop, each participant received a booklet of the teaching material, which was developed according to an intensive literature review [8, 10, 37, 49–51] and the nurses' needs that were identified through interviews. Furthermore, a list of job crafting activities was distributed. This list was developed by the researchers according to a previous job crafting study [31, 32, 52] and input from interviews. This list contained four sections. The first section included a set of points to increase job resources, such as "Asking for help from your colleague or your leaders if you need it" and "Clean your desk to work more efficiently." The second section included a set of points to increase challenging job demands, such as "Offer to be responsible for making the nursing schedule in a certain month" and "Share your head nurse in writing certain documents e.g., lab-ray or sterilization." The third section includes a set of points

to decrease hindering demands, such as “Checking emails only at certain times during the day” and “Encourage patient to perform daily morning care by himself.” The fourth section included five potential nursing situations with suggested job crafting activities. Each situation was accompanied by activities that can increase resources, increase challenging demands, and decrease hindering demands. Giving a list of job crafting activities makes it easier for nurses to practice job crafting [32]. After finishing the workshop, the participants were asked to engage in job crafting activities for 3 weeks guided by the job crafting activity list and the plan developed by the researchers. The participants were then asked to target activities related to increasing resources, optimizing job demands, and seeking challenges in weeks 1, 2, and 3, respectively. During this 3-week intervention period, the participants were invited to a WhatsApp group, which was formed to encourage, guide, share experiences, and send reminders twice weekly to engage in the assigned behaviors. After completing the 3-week intervention program, a reflection session was held. In this session, participants were asked to evaluate their success, obstacles, solutions, and future plans for how they can craft their job. At the end of the session, the researcher expressed appreciation to each group member.

3.6. Control Group.

In the control group, the participants received only the content provided in the first and second sessions. They neither participate in the Michigan Job Crafting Exercise nor prepare the Personal Crafting Plan. Unlike the intervention group, the control group was not required to participate in the 3-week job crafting intervention or the reflection session.
